8.4.3	.3	Biochemistry	.25
8.4.4		Vital Signs, Height and Weight	.25
8.4.5		Physical Examination	.25
9	Analysis So	oftware	.26
10	Changes in	Statistical Analysis Plan	.26

List of Abbreviations

ADA	Adenosine deaminase
ADA-SCID	Adenosine deaminase deficient severe combined immunodeficiency
AE	Adverse event
ALT	Alanine aminotransferase
AST	Aspartate aminotransferase
AXP	Total adenine ribonucleotide
AUC	Area under the curve
BM	Bone marrow
BMT	Bone marrow transplant
cDNA	Complementary Deoxyribonucleic Acid
CHLA	Children's Hospital Los Angeles
CI	Confidence interval
CMV	Cytomegalovirus
CNS	Clinically not significant
CS	Clinically significant
dAXP	Adenine deoxyribonucleotide
DFSP	Dermatofibrosarcoma protuberans
DNA	Deoxyribonucleic acid
ECG	Electrocardiogram
eCRF	Electronic case report form
EFS	Elongation Factor 1α Short form
ERT	Enzyme replacement therapy
GOSH	Great Ormond Street Hospital
HIV	Human immunodeficiency virus
HLA	Human leukocyte antigen
HSC	Hematopoietic stem cell
HSCT	Hematopoietic stem cell transplant
IgA	Immunoglobulin A
IgG	Immunoglobulin G
IgM	Immunoglobulin M
IgRT	Immunoglobulin replacement therapy
LV	Lentiviral vector
MCH	Mean corpuscular haemoglobin
MCHC	Mean corpuscular haemoglobin concentration
MCV	Mean corpuscular volume
MedDRA	Medical Dictionary for Regulatory Activities
MMRM	Mixed model for repeated measures
MUD	Matched unrelated donor
NIH	National Institutes of Health
NK	Natural Killer

Final Version 4.0 Page 5 of 27

PBMC	Peripheral blood mononuclear cells
PCR	Polymerase chain reaction
PEG	Polyethylene-glycol
PHA	Phytohemagglutinin
PRP	Polyribosylphosphate
PT	Preferred Term
RBC	Red blood cell(s)
RCL	Replication competent lentivirus
SAE	Serious Adverse Event
SCID	Severe combined immunodeficiency
SI	Stimulation index
SOC	System Organ Class
TCR	T-cell receptor
TD	Transduction
TREC	T-cell receptor excision circle
UCLA	University of California, Los Angeles
WBC	White blood cell(s)

Final Version 4.0 Page 6 of 27

1 Introduction

The trial assesses a new breakthrough therapy composed of *ex vivo* genetically modified CD34⁺ hematopoietic stem cells (HSC) for the treatment of severe combined immunodeficiency due to adenosine deaminase deficiency (ADA-SCID).

The investigational new drug product, OTL-101, includes autologous bone marrow (BM) CD34⁺ HSC from ADA-SCID infants, children and adolescents, transduced *ex vivo* with a self-inactivating HIV-1 based lentiviral vector encoding the human ADA cDNA (EFS-ADA LV). OTL-101 is used as fresh cell dispersion for infusion after a single non-myeloablative conditioning.

2 Study Design

This is a historically controlled, open-label, prospective, non-randomized Phase I/II clinical trial to assess the safety and efficacy of OTL-101.

OTL-101 will be compared to an historical control group treated with allogeneic Hematopoietic Stem Cell Transplantation (HSCT), representative of standard of care.

Two centres are involved in this study: UCLA and the National Institute of Health (NIH) in Bethesda, MD. Nineteen subjects have been treated at UCLA and one at the NIH.

Final Version 4.0 Page 7 of 27

3 Study Schedule

Evaluation	Scr	B-L	Pre- op	Infus	DII	+1d	Months After Procedure												
				ion	BU		1	2	3	4	5	6	8	10	12	15	18	21	24
P.E.	X	X	_		_	X	X	X	X	X	X	X	X	X	X	X	X	X	X
History	X	X	-		-	X	X	X	X	X	X	X	X	X	X	X	X	X	X
Comprehensive Metabolic Panel ^a	X	X	X		-	X	X	X	X	X	X	X	X	X	X	X	X	X	X
Magnesium, phosphate	X	-	X		-	-	-	-	-	-	-	-	-	-	-	-	-	-	-
CBC with diff.	X	X	X		-	X	X	X	X	X	X	X	X	X	X	X	X	X	X
Cytogenet. PB	X	-	-		-	-	-	-	-	-	-	-	-	-	-	_	-	-	-
Pregnancy test*	X	-	-		X	-	-	-	-	-	-	-	-	-	-	-	-	-	-
INR or PT/PTT	X	-	X		-	-	-	-	-	-	-	-	-	-	-	-	-	-	-
Type and cross	-	-	X		-	-	-	-	-	-	-	-	-	-	-	-	-	-	-
HIV-1, HepB & C, CMV, B19	X	-	-		-	-	-	-	-	-	-	-	-	-	-	-	-	-	-
Urinalysis	X	-	X		-	-	-	-	-	-	-	-	-	-	-	-	-	-	-
ECG	X	-	-		-	-	-	-	-	-	-	-	-	-	-	-	-	-	-
Echo	X	-	-		-	-	-	_	-	-	-	-	-	-	-	_	-	-	-
CXR	X	-	-		-	-	-	-	-	-	-	-	-	-	-	-	-	-	-
Pulse ox.	X	-	-		-	-	-	-	-	-	-	-	-	-	-	-	-	-	-
RBC dAXP	-	X	-		-	-	X	X	X	X	X	X	X	X	X	X	X	X	X
RBC ADA activity	-	X	-		-	-	X	X	X	X	X	X	X	X	X	X	X	X	X
Immune function ^b	-	X	-		-	-	X	X	X	X	X	X	X	X	X	X	X	X	X
TREC, TCRV β panel	-	X	-		-	-	-	-	-	-	-	X	-	-	X	-	X	-	X
PBMC for RCL ^c	-	X	-		-	-	-	-	X	-	-	X	-	-	X	_	_	_	X

Final Version 4.0 Page 8 of 27

Serum for WB to RCL ^d	-	X	-	-	-	•	-	X	-	-	X	•	-	X	-	•	ı	X
PBMC for vector ^c	-	X	-	-	-	X	X	X	X	X	Xg	X	X	Xg	X	Xg	X	Xg
Busulfan PK ^e	-	-	-	X	-	-	-	-	-	-	-	-	-	-	-	-	ı	-
Myelosupp. Labf	-	-	-		X	X	-	-	-	-	-	-	-	-	-	-	-	-

Scr = screen

B-L = Baseline

+1d = day after infusion

BU = Busulfan: See Appendix C for details of administration

X = to be performed, -= not to be performed

*For female subject of child-bearing potential

aincludes albumin, AST/ALT, alkaline phosphatase, total protein, total bilirubin, creatinine, BUN, glucose, calcium, Na+, K+, Cl-, total CO2

bincludes lymphocyte subsets phenotype, quantitative immunoglobulins, antibodies to Tet/PRP (Q 3 months if not receiving IVIg), T cell proliferation to PHA/Tet (only at 6, 12, 18, and 24 months and only to Tet if immunized against tetanus).

^cAt each time, any unused PBMC will be cryopreserved in liquid nitrogen, for possible future studies.

^dTo be banked for possible future studies

^eBusulfan PK at 0, 1, 2, 4, 8, 13 hours following IV Busulfan administration, done during hospitalization

^fMyelosuppression Laboratory: Hepatic function tests, CBC/Diff, 2x per week for up to 6 weeks, from day +1 until hospital discharge when neutrophil recovery is observed, or longer as indicated. For subjects who have slow recovery of counts after transplant (beyond Day +30), CBC/Diff will be performed at least once every 7-10 days until ANC is >500 cells/mm.³

gAccording to current FDA guidelines, LAM-PCR samples will be obtained ≈ every 6 months, for 5 years, then annually for an additional 10 years

Final Version 4.0 Page 9 of 27

4 Study Objectives

4.1 Primary Objectives

Study: NCT01852071 - UCLA Fresh

The primary objectives in this study are:

- to examine the safety of autologous transplantation of bone marrow CD34⁺ cells transduced with the EFS-ADA lentiviral vector (OTL-101). The safety review will include the identification of grade III/IV serious adverse events (SAE). Subjects will also be monitored for clinical toxicities, replication competent lentivirus, and monoclonal expansion at regular intervals by a clinician, as well as standard blood counts and chemistries.
- to estimate overall and event-free survival by 12 months where failure is defined by one of the following endpoints: death; reinstitution of PEG-ADA; or performance of an allogeneic BMT.

4.2 Secondary Objectives

The secondary objectives will assess the efficacy of OTL-101, engraftment of transduced cells and the extent of ADA expression and immune reconstitution. The secondary outcomes will:

- 1. Assess overall and event free survival at 24 months,
- 2. Compare overall survival and event free survival at 24 months between patients treated with OTL-101 and patients treated with allogeneic HSCT,
- 3. Assess the extent of gene transfer in peripheral blood cells,
- 4. Assess ADA gene expression by measuring ADA enzymatic activity and adenine nucleotides.
- 5. Examine the effects of reconstituting ADA gene expression on immune function through serial examination of peripheral blood leukocytes and myeloid cells,
- 6. Assess immune reconstitution and infection rates, and
- 7. Assess use of immunoglobulin replacement therapy.

5 Endpoints

5.1 Primary Endpoints

The primary endpoints are:

- Safety: the incidence and severity of serious adverse events (SAEs)
- Efficacy: overall and event-free survival at 12 months, where events are death, reinstitution of PEG-ADA therapy and performance of an allogeneic BMT.

5.2 Secondary Endpoints

Secondary endpoints for this study are:

- Overall survival and event-free survival at 24 months
- Efficacy of gene transfer/engraftment of HSC
- ADA expression: enzyme activity and detoxification

Final Version 4.0 Page 10 of 27

- Effects on ADA reconstitution on immune phenotype and function (the need for IgRT will be assessed under this category)
- Immune reconstitution
- Infection rates

6 Timing of Analyses

The statistical analyses of data from this study will be performed in three stages:

Interim look:

- Performed after all subjects have completed 6 months of follow-up post infusion
- Descriptive statistics for all available data
- Comparisons between OTL-101 treated subjects and HSCT control cohorts of demographics and overall survival

Primary analysis:

- Performed after all subjects have completed 12 months of follow-up post infusion
- Descriptive statistics for all available data
- Comparison to HSCT control cohorts on overall and event-free survival (primary efficacy endpoints), use of immunoglobulin replacement therapy (IgRT) and infection rate (key secondary endpoints).

End of study analysis:

- Performed after all subjects have completed the study (24 months of follow-up post infusion)
- Descriptive statistics for the complete study cohort
- Comparison to HSCT control cohorts on overall and event-free survival (primary efficacy endpoints), use of immunoglobulin replacement therapy (IgRT) and infection rate (key secondary endpoints).

7 Analysis Populations

7.1 Efficacy Population

The primary efficacy population will consist of all patients treated with OTL-101 at UCLA/NIH (current study cohort).

The primary efficacy population from the HSCT historical control cohort will consist of ADA-SCID patients without a medically eligible HLA-matched sibling/family donor and treated with HSCT at either Great Ormond Street Hospital (GOSH) or Duke University from the year 2000 onwards.

Final Version 4.0 Page 11 of 27

Additional efficacy comparisons will be made with:

- ADA-SCID patients with matched related donors treated with HSCT at either GOSH or Duke University from the year 2000 onwards;
- the complete HSCT historical control cohort consisting of ADA-SCID patients with any type of donor treated with HSCT at either GOSH or Duke University from the year 2000 onwards.

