In this multicenter retrospective study, the authors analyzed outcome of HCT in 106 patients with ADA-SCID who received a total of 119 transplants. HCT from matched sibling and family donors (MSD, MFD) had significantly better overall survival (OS) (86% and 81%) in comparison to HCT from matched unrelated (66%; $p < 0.05$) and haploidentical donors (43%; $p < 0.0001$). Superior OS was also seen in patients who received unconditioned transplants in comparison to myeloablative procedures (81% vs. 54%; $p < 0.003$) although in unconditioned haploidentical donor HCT, non-engraftment was a major problem. Long term immune recovery showed that regardless of transplant type, overall T cell numbers were similar although a faster rate of T cell recovery was observed following MSD/MFD HCT. Humoral immunity and donor B cell engraftment was achieved in nearly all evaluable surviving patients and was seen even after unconditioned HCT. These data detail for the first time the outcomes of HCT for ADA-SCID and demonstrate that if patients survive HCT, long term cellular and humoral immune recovery is achieved. These outcomes confirm many previous smaller reports on the rates of success and complications for different types of allogeneic HSCT for ADA-deficient SCID.

Thus, while T cell-depleted or unrelated adult donor or cord blood HSCT have become useful treatment modalities for ADA-deficient SCID patients, they are still beset by a number of serious limitations. Because of these limitations, haploidentical or matched unrelated BMT are generally not offered as options for ADA-SCID. The two conventional treatment options are HLA-identical related BMT for those with available matched siblings and ADA enzyme replacement therapy in the form of PEG-ADA for most others.

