5 STUDY POPULATION

5.1 Description of the Study Population

Number of subjects to be studied:

A total of twenty (20) subjects will be treated under this protocol. Eligible subjects will be children \geq 1.0 months of age with a diagnosis of ADA-deficient SCID, lacking a medically eligible HLA-matched sibling donor and meeting defined inclusion/exclusion criteria related to medical status and organ function (*vide infra*).

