5.1.1 Participant Inclusion Criteria

Inclusion criteria:

Participants must satisfy Inclusion Criteria I, II, and III.

I. Children \geq 1.0 months of age with a diagnosis of ADA-deficient SCID based on:

- A. Decreased ADA enzymatic activity in erythrocytes, leukocytes, skin fibroblasts, or in cultured fetal cells to levels consistent with ADA-deficient SCID as determined by reference laboratory **or** confirmed ADA gene mutation(s) known to cause disease

AND

- B. Evidence of severe combined immunodeficiency based on either:

1. Family history of first order relative with ADA deficiency and clinical and laboratory evidence of severe immunologic deficiency,

OR

2. Evidence of severe immunologic deficiency in subject prior to institution of immune restorative therapy, based on

- a. lymphopenia (absolute lymphocyte count <400 cells/mcL) OR absence or low number of T cells (absolute CD3+ count <300 cells/mcL)

OR

- b. severely decreased T lymphocyte blastogenic responses to phytohemagglutinin (either <10% of lower limit of normal controls for the diagnostic laboratory, <10% of the response of the normal control of the day, or stimulation index <10)

II. Ineligible for matched sibling allogeneic bone marrow transplantation:

Absence of a medically eligible HLA-identical sibling, with normal immune function, who may serve as an allogeneic bone marrow donor.

III. Signed written informed consent according to guidelines of the IRB (UCLA [Office of Human Research Protection Program](#) and National Human Genome Research Institute (NHGRI) Institutional Review Board

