6 STUDY AGENT/INTERVENTIONS

The Investigational New Drug to be tested is autologous CD34+ cells transduced *ex vivo* with a lentiviral vector based upon the self-inactivating (SIN) lentivirus (HIV-based LV): EFS-ADA

(referred in this document as OTL-101). The vector has been produced as cell-free lentiviral supernatant from the 293T cell line, and has an envelope pseudotype from the vesicular stomatitis virus (VSV). The vector will be used for *ex vivo* transduction of CD34+ progenitor cells from the bone marrow of infants or children with adenosine deaminase (ADA)-deficient severe combined immunodeficiency (SCID). OTL-101 will be subsequently infused intravenously after a single non-myeloablative dosage of busulfan (4 mg/kg intravenously x1).

This is a Phase I/II Clinical Trial to evaluate the safety (as primary endpoint) and efficacy (as secondary end-points) of the addition of a normal human ADA cDNA by the EFS-ADA lentiviral vector to bone marrow CD34+ stem/progenitor cells. Due to the natural course of the disease, these patients require some form of treatment and with that in mind, a placebo group would be unethical. At the current time, the standard of care is a matched sibling allogeneic bone marrow transplantation, when a medically-suitable donor exists. Since our agent is still under investigation, if a patient has an HLA matched sibling and qualifies for a bone marrow transplantation, they will be excluded from our study. The other current treatment options have their drawbacks and limitations, including high financial cost, need for regular IM injections (PEG-ADA) or GVHD, dysfunctional immune system, and death from unrelated or mismatched HSCT (described in more details above).

An "Appendix M" has been submitted to the Recombinant DNA Advisory Committee (RAC) as per the Office of Biological Activities (OBA), RAC guidelines and unanimous RAC recommendation for approval was obtained on Dec 2, 2009 (#0910-1006).

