11.2 Design Considerations and Data

This is a subject-level historically controlled, prospective, non-randomized Phase I/II clinical trial to assess the safety and efficacy of autologous transplantation of CD34+ cells originated from the bone marrow of ADA-SCID infants and children following human ADA cDNA transfer by the EFS-ADA lentiviral vector.

Descriptive results will be presented for the study cohort.

Comparisons will be made to three cohorts:

- 1) A historical control group consisting of ADA-SCID HSCT-treated subjects lacking a medically eligible HLA-matched sibling/family donor and treated at GOSH/UCL (UK) or Duke University Children's Hospital, North Carolina Transplant Center (USA) from the year 2000 onward
- 2) A historical control group consisting of ADA-SCID HSCT-treated subjects having a medically eligible HLA-matched sibling/family donor and treated at GOSH/UCL (UK) or Duke University Children's Hospital, North Carolina Transplant Center (USA) from the year 2000 onward
- 3) All HSCT-treated subjects from GOSH/UCL or Duke University Children's Hospital, who were treated with HSCT from the year 2000 onward, with any type of donor

Details on the historical HSCT control groups from GOSH/UCL and Duke University Children's Hospital can be found in [Appendix H](#).

Statistical analyses will be performed, and their outcomes presented, in three stages:

- Interim look – 6 months
 - Descriptive statistics for all available subjects
- Primary analysis - Comparison on primary efficacy endpoints to the HSCT control cohorts—12 month follow-up analysis
 - Descriptive statistics for the complete study cohort, with all patients having reached at least 12 month follow-up
 - Comparison to HSCT control cohorts on safety, primary efficacy endpoints and need of immunoglobulin replacement (IgRT) (main secondary efficacy endpoint).
- End of study analysis:
 - Descriptive statistics for the complete study cohort, with all patients having completed the study (24-month follow-up)
 - Comparison to HSCT control cohorts on safety, primary efficacy endpoints and need of immunoglobulin Replacement (IgRT) (main secondary efficacy endpoint).

In each study stage and for all analyses, all relevant data available will be used.

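### The primary HSCT control set removes patients with a matched non-sibling family donor, whom trial eligibility admits, and no planned control set follows the eligibility rule

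*SAP*

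**What the plan says.** **Trial entry.** Three places in the protocol make a matched sibling the only donor-related bar. Inclusion criterion II (5.1.1) reads: "Absence of a medically eligible HLA-identical sibling, with normal immune function, who may serve as an allogeneic bone marrow donor". Section 5.1 describes the subjects as "lacking a medically eligible HLA-matched sibling donor". Section 6 says that "if a patient has an HLA matched sibling and qualifies for a bone marrow transplantation, they will be excluded from our study". The exclusion criteria in 5.1.2 do not mention other matched relatives.

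**Primary controls.** SAP 7.1 takes patients "without a medically eligible HLA-matched sibling/family donor" who received HSCT at GOSH or Duke from 2000 onward. Protocol 11.2 has the same rule ("ADA-SCID HSCT-treated subjects lacking a medically eligible HLA-matched sibling/family donor"), and so does 11.5.2. SAP 8.3 makes the set without a matched related donor the primary comparator for all efficacy analyses.

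**Other controls.** Two further sets are planned: controls with a matched related donor, in which siblings and other relatives are pooled, and all controls with any donor.

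**A different wording.** Protocol 11.6.3 (Primary Analysis) divides the controls by whether they had a matched related sibling donor. That is not the split in 11.2, 11.5.2 or the SAP.

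**The concern.** With historical controls and no randomisation, the comparison is only as credible as the match between the controls and the trial's own entry rule. Here the two groups follow different donor rules. The controls who are removed belong to the donor category with the best reported survival among those that trial eligibility admits: Protocol 2.1.3.1(e) reports that transplants from matched sibling and matched family donors "had significantly better overall survival (OS) (86% and 81%) in comparison to HCT from matched unrelated" donors, and than haploidentical donors.

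At stake is the estimated OS and EvFS difference against HSCT. The primary comparison does not quite ask how children eligible for OTL-101 would have fared with HSCT; it asks this of a subset expected to do worse.

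**Working it through.** **1. The protocol's own figures.** Summing the centre rows of Table 1 (Protocol 2.1.3.1) gives 27/30 = 90.0% alive for matched sibling and family donors pooled, 5/8 = 62.5% for matched unrelated and 21/42 = 50.0% for haploidentical. These reproduce the printed totals. Table 1 does not separate siblings from other family; the multicentre report in 2.1.3.1(e) does: sibling 86%, other family 81%, matched unrelated 66%, haploidentical 43%.

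**2. The control sets side by side.**

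| Control's donor | Allowed by trial donor rule | Primary set | Matched-related set | All-donor set |
|---|---|---|---|---|
| Matched sibling | no | no | yes | yes |
| Matched non-sibling family | yes | no | yes | yes |
| Matched unrelated | yes | yes | no | yes |
| Haploidentical | yes | yes | no | yes |

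No planned set has the pattern in the second column.

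**3. Size of the shift in control OS.** Let *f* be the share of matched non-sibling family donors among controls without a matched sibling, and *h* the haploidentical share of the rest. The documents give neither, so both are assumptions.

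- Primary-set OS: p = 0.66(1 − h) + 0.43h
- Eligibility-matched OS: (1 − f)p + 0.81f
- Shift: f(0.81 − p)

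| f | h = 30% (p = 59.1%) | h = 50% (p = 54.5%) | h = 70% (p = 49.9%) |
|---|---|---|---|
| 0% | 0 | 0 | 0 |
| 10% | 2.2 | 2.7 | 3.1 |
| 20% | 4.4 | 5.3 | 6.2 |
| 30% | 6.6 | 8.0 | 9.3 |
| 40% | 8.8 | 10.6 | 12.4 |

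Example: with f = 30% and h = 50%, control OS is 54.5% in the primary set and 0.7 × 54.5 + 0.3 × 81 = 62.5% in the eligibility-matched set.

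With f still at 10–40%, more extreme mixes widen the range. If the rest are all matched unrelated (p = 66%), the shift is 1.5 to 6.0 points; if all haploidentical (p = 43%), 3.8 to 15.2 points. For scale, SAP 8.3.1.1 uses a 10-point margin in its non-inferiority-like probability.

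**4. Do the planned sets bracket the answer?** Adding siblings at 86% to the example, at an assumed 20% of all controls, gives 0.8 × 62.5 + 0.2 × 86 = 67.2%. The expected order is primary 54.5%, eligibility-matched 62.5%, all-donor 67.2%. The matched-related set, between 81% and 86%, lies higher still.

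**5. Would the conclusion change?** This is an illustration only; Fisher's exact test is not in the SAP. Applying the Table 1 share of unrelated and haploidentical donors (50/80) to the 25 + 10 = 35 controls in Appendix H gives about 22 primary controls.

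- Suppose 20/20 survive on OTL-101 and 11/22 in the primary set: difference 50 points, p = 0.0002. Adding 6 family-donor controls with 5 alive gives 16/28: difference 43 points, p = 0.0005. The posterior probability of superiority under the SAP's Beta(1,1) priors stays above 0.999.
- Suppose 19/20 survive and the control rate is close to the matched-unrelated figure, 15/22: difference 27 points, p = 0.047. With 20/28 it is 24 points, p = 0.061. With 8 added controls (21/30), p = 0.037, so crossing 0.05 here reflects small counts rather than a steady trend.

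**The case against.** The strongest reply has four parts.

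- **The share may be zero.** The documents do not say how many of the 25 GOSH and 10 Duke controls had a matched non-sibling family donor. If none did, nothing changes. This stands, and the range must start at zero.
- **The planned set may already fit the treated children.** If no OTL-101 subject had such a donor, the primary set mirrors the treated cohort on donor availability, and adding family-donor controls would introduce a mismatch. This also stands. The planned baseline summaries cannot settle it: SAP 8.2.4 covers sibling HLA match and the unrelated donor or cord search, but no other relatives.
- **The all-donor comparison is already planned.** On the protocol's figures it is conservative for OTL-101, so the eligibility-matched result is bracketed and nothing is hidden. This is correct, but a bracket is not an estimate, and its upper side depends on siblings, who cannot enter the trial.
- **The comparison is not the trial's main objective.** The primary efficacy objective is to estimate OS and EvFS at 12 months; comparison with HSCT is listed as a secondary objective at 24 months. This limits the weight of the point. However, Protocol 11.2 and SAP 6 make the comparison part of the 12-month primary analysis.

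A reader might infer that the bias always favours OTL-101. The documents do not support that. The direction is an expectation from multicentre OS rates, which the protocol does not report as restricted to these two centres, to transplants from 2000 onward or to 12 months. No rates by donor type are given for EvFS. A reader might also infer that a regulator agreed the donor split. Protocol Appendix I and SAP 10.2 record agreement or approval only for using the Duke data.

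**Conclusion.** The mismatch is in the text: entry turns on a matched sibling, the primary control set on any matched relative, and Protocol 11.6.3 on a sibling again. No planned control set equals the absence of a matched sibling.

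The expected effect on the OS comparison favours OTL-101. It is zero if no control had a matched non-sibling family donor, and about 2 to 12 points if such donors make up 10–40% of controls without a matched sibling and haploidentical donors 30–70% of the rest. Both shares are assumptions; the rates are the protocol's. The size for EvFS is unknown.

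It would go too far to conclude that a finding of superiority depends on this choice, or that the primary set must be replaced. In the main illustration the difference falls from 50 to 43 points and the conclusion holds; what is exposed is the size of the estimate. A control set without matched related donors is a coherent choice. The gap is that the set matching eligibility is never analysed.

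**What to change.** 1. Reconcile Protocol 11.6.3 with Protocol 11.2 and 11.5.2 and with SAP 7.1 and 8.3, so that one donor rule defines the primary control set.
2. Confirm that the donor-type field separates siblings from other family. Appendix H and SAP 8.2.16 list donor type, but neither says how it is coded.
3. Add to SAP 7.1 and 8.3 a named control set defined by the trial's own criterion, no medically eligible HLA-matched sibling donor. Use it as a sensitivity analysis for OS and EvFS at 12 and 24 months, with the methods already planned for the other sets.
4. Report how many controls had a matched non-sibling family donor. If the number is zero, the sensitivity set coincides with the primary set and the question is closed.

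The cost is one more control grouping in the tables and a treatment difference that may be less favourable to OTL-101. If the donor field does not separate siblings from other family, the matched-related controls would need to be re-coded from source records.
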